#### 6.13.4. Vital Signs

The Baseline-OL value, the actual value and change from Baseline-OL for the Week 56, Week 78, Week 104 visits, and for the last available on-treatment value will be summarized by treatment history, with the Baseline-OL value being defined as the last non-missing value prior to first dose of the open-label treatment phase study drug.

A tabular summary of subjects with PCS vital sign changes from Baseline-OL will be prepared analogously to the double-blind treatment phase table (see Section 5.12.4). When the PCS values are summarized, assessments after the first dose of the open-label treatment phase, that have been assigned to Week 52 by using the visit windowing (see Section 6.6), will be analyzed as Week 56 values.

#### 6.13.5. Physical and Neurological Examinations

The summaries from the double-blind treatment phase (see Section 5.12.5) will be repeated for the Safety-OL population and extended by the visits Week 56, Week 78, and Week 104.

#### 6.13.6. Ophthalmological Examination

The summary from the double-blind treatment phase (see Section 5.12.6) will be repeated for the Safety-OL population.

The subject data listing prepared for the double-blind treatment phase (see Section 5.12.6) will be extended by the open-label treatment phase visit(s). An additional flag will be added to indicate the entries of the open-label treatment phase.

Sponsor:	TauRx Therapeutics Ltd.		
Protocol:	TRx-237-039		
Document Version No.:	3.0	Document Date:	07-JUN-2023

## 7. PLASMA BIOMARKER ANALYSIS

The analysis described in this section is based on version 2.2 from 16-MAR-2023 of the TRx-237-039 Secondary Research Plan “Plasma Biomarker Analysis”, in which a detailed background, scientific rationale, and sample size justification is given.

The following analysis are all exploratory of nature. The analyses stand on their own and corresponding nominal p-values will be reported and no correction for multiple comparisons will be conducted.

A subject data listing of the biomarkers will be provided.

The tau fragment analysis, which was introduced with the version 2.1 of the Secondary Research Plan, is based on a subset of pre-dose Baseline back-up PK plasma samples is not part of this SAP. This analysis will be performed by the University of Aberdeen (Scottish Biologics Facility).

### 7.1. Biomarker

The initial analysis focuses on the following primary exploratory biomarkers, which will be analyzed in the framework of primary and secondary biomarker endpoints:

- Tau phosphorylated at residue 181 (P-tau181)
- Neurofilament light (NfL)

The null hypotheses for each of these biomarkers are, that there is no difference from Baseline to Week 52 visit within the HMTM group and that HMTM does not have an impact on change of the respective endpoint from Week 52 to Baseline compared to control. For correlations between biomarkers and between other clinical study endpoints (see Section 7.3.3), the null hypothesis is that there is no correlation between those.

The following potential biomarkers are ‘other’ exploratory biomarker research and will be analyzed analogously to the primary exploratory biomarkers upon request, with T-tau being planned to be analyzed with version 2.2 of the Secondary Research Plan:

- Tau phosphorylated at residue 231 (P-tau231)
- Core-proline tau
- Total tau (T-tau)
- Glial fibrillary acidic protein (GFAP)

There is no prior evidence to show that these biomarkers will show a pharmacodynamic response to treatment with HMTM nor any other approved or investigational drugs for AD. Given this, no hypotheses are provided, but the above null-hypothesis apply here as well.

Sponsor:	TauRx Therapeutics Ltd.		
Protocol:	TRx-237-039		
Document Version No.:	3.0	Document Date:	07-JUN-2023

---

For the avoidance of doubt, even in the cases where a clear hypothesis exists which direction the change should take, all tests will be conducted at the two-sided, 0.05 level of significance.

#### 7.1.1. Biomarker Samples

The investigated (potential) biomarkers are pre-analyzed in different companies and institutions: P-tau 181 and P-tau231 (Medpace Inc.), NfL (Drug Development Solutions Ltd.), Core-proline tau (University of Aberdeen Good Laboratory Practice Test Facility), T-tau (University College London Consultants Ltd.), and GFAP (*to be decided*). Due to different processing schedules, the pre-processed data will be provided to Cytel in batches and therefor the statistical analysis will be performed in batches.

Plasma samples have been taken at Baseline, Week 4, Week 52, and Week 104 visits, on three occasions: pre-dose, approximately 1 to 2 hours post-dose, and approximately 4 hours post-dose.

The biomarker data analysis is based on back-up PK plasma samples taken pre-dose during the Baseline and Week 52 visits.

On a subject level: If the pre-dose sample is unavailable, the earliest available post-dose sample (first: 1-2 hours post-dose, second: 4 hours post-dose) will be used; and furthermore, if the back-up plasma sample is unavailable the residual primary PK plasma will be utilized instead, if available. If no proper sample is available, the value is set to missing. This means, the order of samples is as follows:

- Back-up sample: 1. Pre-dose, 2. 1-2 hours pose-dose, 3. 4 hours post-dose
- Residual primary sample: 4. Pre-dose, 5. 1-2 hours pose-dose, 6. 4 hours post-dose
- 7. "Missing"

The first sample which is available will be used for the analysis. This means, for the avoidance of doubt, the analysis will be performed based on all available samples, irrespective of the actual sample used. Thus, pre-dose versus post-dose samples as well as primary versus back-up samples will be used alike. The only relevant characteristic of the sample is, which is used in the analysis, if it is Baseline or Week 52 visit.

Possible reasons for unavailability of a plasma sample are:

- More than one previous freeze-thaw cycle.
- An approximate hemoglobin concentration of 250 mg/dL or more.
- Incorrect collection of a sample.

For completeness, a summary table will be provided, that shows the number of samples used for each biomarker presented by treatment group and total, that were Baseline pre-dose, Baseline 1-2 hours post-dose, Baseline 4 hours post-dose, Week 52 pre-dose, Week 52 1-2 hours post-dose, and Week 52 4 hours post-dose. If needed, this will be further separated by back-up sample and primary sample.

Sponsor:	TauRx Therapeutics Ltd.		
Protocol:	TRx-237-039		
Document Version No.:	3.0	Document Date:	07-JUN-2023

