- l At Visits 2, 3, and 7, blood will be collected on *the same day on three occasions*, pre-dose and again approximately 1 to 2 hours post-dose (these should be morning appointments); and a third sample with time of dose and sample at approximately 4 hours after the dose. Note: The time of the dose from the previous day must be collected and recorded at Visits 3 and 7, in addition to the time of the dose given in the clinic. For any ET visit, if the subject has not yet discontinued study drug and is willing to take a final in-clinic dose, three blood samples will be collected as described above. If, however, the subject has already discontinued study drug or is unwilling to take a final in-clinic dose, a single blood sample only for determination of MT concentrations will be collected, irrespective of the date or time of the last dose of study drug. The date and time of last dose must be collected and recorded. If a subject has discontinued study drug but wants to continue to attend study visits off-treatment (the off treatment on study [TOTOS] group), then MT concentration blood samples will not continue to be collected.
- m A single blood sample for *ApoE* can be collected any time after eligibility for randomization and continued participation in the study has been confirmed (but prior to Visit 7, the end of the double-blind treatment period) for subjects who provide legally acceptable consent.
- n These are to be rated by the same rater, where possible, as at Screening, after all other efficacy assessments have been completed. MMSE and CDR assessments will be subject to central review by MedAvante-ProPhase clinicians in the native language.
- o The clinical efficacy scale assessments should be performed at approximately the same time of day throughout the study for a given subject, to the greatest extent possible.
- p In-clinic dose at Visit 7 to be taken after pre-dose assessments, from newly dispensed Visit 7 open-label study drug kit (see Table 10-3 for the pre-dose and post-dose assessments to be performed at Visit 7).

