## 7.3. Statistical Analysis of Biomarker Outcomes

The following analysis will be performed based on the Biomarker Population.

Week 52 samples taken after the first day of the open-label treatment phase will not be used in the analysis.

Since from protocol version 5 on, the control group had occasional spiking with 4mg MTC with an average frequency of twice per week, it is therefore of interest to test not only the doses of HMTM compared to control, but also to a subpopulation of control that showed lowest predicted concentrations of parent MT at Week 52. A threshold of  $\leq 0.1$  ng/mL for predicted Week 52 steady-state ( $C_{max,ss}$ ) parent MT concentration will be used to define the lowest parent MT group. In the analysis output the control group will be presented as "MTC 8 mg/week".

The actual received treatment and the actual (verified) values of the randomization stratification variables will be used in the analysis.

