### 7.4. Future Sample Analysis

If evidence of a beneficial treatment effect of HMTM is apparent for any of the biomarkers, further analysis at all other timepoints (Week 4 and Week 104) for that biomarker will be performed. In such an event, this analysis will be confirmed by amendment to the biomarker research plan, to the test-site-specific plans, and to this SAP, as appropriate.

If beneficial treatment effect of HMTM is apparent for any of the biomarkers, further sample analysis would be required to show pre-dose and post-dose samples are equivalent for that biomarker.

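### The biomarker sample order lets a control subject's Week 52 value be drawn after the first open-label HMTM dose, and a Baseline value after the first study dose, ahead of any usable residual pre-dose sample.

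*SAP*

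**What the plan says.** SAP 7.1.1 bases the biomarker analysis on back-up PK plasma drawn pre-dose at Baseline and Week 52. It then gives a fallback: "If the pre-dose sample is unavailable, the earliest available post-dose sample (first: 1-2 hours post-dose, second: 4 hours post-dose) will be used". The full order is spelled out in two lines. First: "Back-up sample: 1. Pre-dose, 2. 1-2 hours pose-dose, 3. 4 hours post-dose". Then: "Residual primary sample: 4. Pre-dose, 5. 1-2 hours pose-dose, 6. 4 hours post-dose". A seventh place is missing. The section treats the types as interchangeable ("Thus, pre-dose versus post-dose samples as well as primary versus back-up samples will be used alike") and names the visit as the sole property that counts: "The only relevant characteristic of the sample is, which is used in the analysis, if it is Baseline or Week 52 visit".

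SAP 7.3 contains one timing restriction: "Week 52 samples taken after the first day of the open-label treatment phase will not be used in the analysis".

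On dosing at Week 52, a footnote to Protocol Table 10-2 reads: "In-clinic dose at Visit 7 to be taken after pre-dose assessments, from newly dispensed Visit 7 open-label study drug kit". Protocol 12.2 says the same, and gives the open-label regimen for all subjects as two 4-mg tablets in the morning and two in the evening. (The protocol calls the drug LMTM, the SAP HMTM.)

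SAP 7.4 says that, if a beneficial effect is seen for a biomarker, "further sample analysis would be required to show pre-dose and post-dose samples are equivalent for that biomarker".

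**The concern.** The rule looks neutral because it is the same in all arms, but the dose that precedes a post-dose sample does not mean the same thing in each arm. At Week 52 the control group's post-dose samples follow its first HMTM. At Baseline a post-dose sample follows HMTM in the active arms and placebo or MTC tablets in control. A fallback sample can therefore differ in drug exposure along the randomized comparison that the model estimates.

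The order also places both post-dose back-up samples above a residual primary pre-dose sample. A post-dose value can thus be chosen when a usable pre-dose value from the same morning exists. At stake are the exploratory comparisons of change in P-tau181 and NfL, and any further marker analyzed the same way. SAP 1.1 says the analyses planned in the SAP will go into regulatory submissions and manuscripts.

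**Working it through.** The plan states no figure on this point to reproduce. The check sets the passages side by side and follows the rule through.

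**Inputs**
- Sampling times at Visits 2 and 7: pre-dose, about 1-2 h and about 4 h post-dose (Protocol 10.5.2.4).
- Visit 7 is Day 1 of the open-label phase, and the in-clinic dose is from the open-label kit (Protocol 12.2 and 12.5).
- Open-label morning dose: 2 x 4 mg = 8 mg in every arm (Protocol 12.2).
- Double-blind morning dose: 2 x 4 mg = 8 mg in the 16 mg/day arm; 1 x 4 mg = 4 mg in the 8 mg/day arm; no HMTM in control (Protocol 12.2).
- Control MTC exposure: 2 x 4 mg = 8 mg per week (SAP 1.1).
- Biomarker Population: double-blind completers, excluding subjects off treatment but on study (SAP 7.2).

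**Step 1: a control subject whose pre-dose back-up sample is unavailable at Week 52.** Place 1 fails. Place 2 is the 1-2 h post-dose back-up sample and place 3 the 4 h one. If either is usable, it is taken. A residual primary pre-dose sample is place 4 and is not reached.

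**Step 2: what that sample follows.** It follows the first open-label dose, 8 mg of HMTM. This is the control subject's first HMTM, and nominally equals the arm's whole weekly MTC amount (8 mg against 8 mg). For the 16 mg/day arm the same dose continues the usual regimen (8 mg against 8 mg). For the 8 mg/day arm it is double the usual morning dose (8/4 = 2).

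**Step 3: does SAP 7.3 remove it?** No. The exclusion starts after the first open-label day. A sample drawn 1-4 h after the dose falls on that day.

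**Step 4: does the population definition remove it?** No. Subjects who are off treatment at Week 52 receive no open-label drug (SAP 6.1), but they are the ones excluded from the Biomarker Population. Those who remain and are dosed at Visit 7 are dosed from the open-label kit.

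**Step 5: Baseline.** The same order applies at Visit 2, where a post-dose sample follows the first double-blind dose. SAP 2.3 sets a different general convention: where Baseline has pre- and post-dose assessments, the pre-dose one is used. For laboratory data, SAP 5.12.3 checks sampling time against dosing time on the first-dose day and falls back to Screening if the sample was post-dose. The biomarkers get neither protection.

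**Step 6: do other parts of SAP Section 7 catch it?** SAP 7.1.1 plans a table counting samples by timing and treatment group, but no analysis restricted to pre-dose samples. The equivalence work in SAP 7.4 depends on an apparent benefit, so a contrast made smaller by drug in the control group would not trigger it.

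**The case against.** The strongest case on the other side has five parts.

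- **Exploratory status.** SAP Section 7 is exploratory throughout, with nominal p-values and no multiplicity control. No primary or secondary endpoint depends on it. This stands and limits the weight of the point.
- **No evidence of an acute effect.** Nothing in the documents says that one 8 mg dose moves plasma P-tau181 or NfL within four hours, and the effect could be negligible. A reader might infer that the randomized contrast is contaminated. The documents do not support that. They support only that it could be affected, and SAP 7.4 itself treats pre-/post-dose equivalence as still to be shown.
- **Sample integrity.** Residual primary plasma may already have been thawed for the MT assay, so preferring back-up plasma may be deliberate. The separate research plan, which is not available here, may say so. However, SAP 7.1.1 already counts a sample with more than one previous freeze-thaw cycle, or with too much hemoglobin, as unavailable. A residual sample that reaches place 4 has passed those limits.
- **Disclosure.** The count table and the conditional equivalence check make the practice visible. They do not change which value enters the model.
- **Earlier completers.** The version 7.0 entry in the protocol's summary of changes presents the Visit 7 kit instruction as a clarification. Practice at earlier Week 52 visits cannot be established from the documents.

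Two further inferences go too far. One is that every control subject with a failed pre-dose back-up sample gets a post-HMTM value. If both post-dose back-up samples also fail, the order does reach the residual pre-dose sample. The other is that such a residual sample often exists; the documents do not say how often.

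**Conclusion.** The point holds as a defect in the selection rule. As written, SAP 7.1.1 and 7.3 together allow a control Week 52 biomarker value drawn about 1 to 4 hours after first HMTM exposure, and a Baseline value drawn after the first study dose, in preference to a usable residual pre-dose sample. This rests on the current protocol text for Visit 7 dosing and on reading the SAP 7.3 cut-off literally.

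The size is unknown. The documents give no failure rate for pre-dose back-up samples, no rate of usable residual plasma and no acute effect of a dose on either marker. A reader might try to count affected control subjects by applying a failure rate to the expected completers, but that rate would be an assumption with nothing behind it. The direction of any bias is also unknown. Because the analyses are exploratory the point is not critical, but the plan should be corrected: the rule departs from the SAP's own pre-dose Baseline convention and is easily changed.

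**What to change.** 1. In SAP 7.1.1, change the order to back-up pre-dose, then residual primary pre-dose (subject to the existing freeze-thaw and hemolysis limits), then missing. Remove the statements that pre- and post-dose samples are interchangeable and that only the visit matters.
2. In SAP 7.3, move the Week 52 cut-off from the first open-label day to the first open-label dose, and add the matching rule that Baseline samples drawn after the first study dose are excluded.
3. Keep the present any-sample order as a sensitivity analysis, reported with the sample-count table already planned.

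The cost is revised SAP wording, a changed selection rule in the programming, and some additional missing biomarker values whose number is not known. Where only a post-dose sample has already been assayed, residual pre-dose plasma would have to be assayed or the value set to missing in the main analysis.

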## 7.2. Analysis Population

**Biomarker Population:** subjects randomized under protocol version 5.0 or higher, which completed the double-blind treatment phase, excluding the TOTOS (see Section 4.4). Subjects randomized under a protocol version before version 5 with available biomarker data at Week 52 and completed double-blind treatment phase will be included as well.

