## **17.4 Clinical Efficacy and Imaging Analysis**

The various analyses planned in the study are outlined below. The SAP will be more specific and clearly state which analysis and which model will be applied to what type of data.

Subjects will be analyzed in the treatment group and stratification to which they were randomized unless stated otherwise in potential sensitivity analyses. For safety analyses, treatment assignment will be based on the treatment actually received. If a subject receives an incorrect treatment transiently, he/she will be assigned to the predominant treatment group (*i.e.*, the treatment group for which he/she received the greatest number of doses).

For E-MITT, MI-MITT, and PI-MITT analyses, only valid data will be included in the primary and secondary analyses. In subjects who have initiated treatment with an AChEI and/or memantine, assessments made after initiation of such treatment are not considered valid as they could confound the interpretation of the results and will be excluded. Such subjects and affected assessments will be identified prior to unblinding. Sensitivity analyses will be provided for the primary and selected secondary analyses including all data.

The primary and key secondary analyses will be further restricted by excluding subjects who were randomized under protocols prior to Protocol Version 5.0; this is due to the spiking with MTC in the placebo arm. Sensitivity analyses not applying this restriction will be provided.

Various imaging and clinical efficacy analyses will be handled differently for the FDA and European Medicines Agency (EMA). Summary statistics will be tabulated by visit and treatment group using observed data. ITT, E-MITT, MI-MITT, and PI-MITT population-weighted least squares means (LSM), unless otherwise stated, treatment differences, and 95% confidence intervals will also be included; the population will be determined by the corresponding model, dependent on whether the endpoint is an imaging endpoint or an efficacy endpoint. Where requested, annualized rates will be estimated based on the population-weighted LSM.

All models will include the randomization stratification variables as covariates unless otherwise stated. If the models do not converge because of too few observations for a given randomization stratification variable, the corresponding variable/variables will be removed from the model.

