## 1.3. Study Protocol Versions

The following table shows an overview of the differences in duration, population, sample size and randomization ratios, and planned doses groups between the study protocol versions.

Sponsor:	TauRx Therapeutics Ltd.		
Protocol:	TRx-237-039		
Document Version No.:	3.0	Document Date:	07-JUN-2023

**Table 1** Protocol evolution

	Version 2.1	Version 3.0 – 4.1	Version ≥5.0
Duration of study	6 months (double-blind)	9 months (double-blind)	12 months (double-blind) + 12 months (open-label)
Population	Mild AD  (MMSE 20-25)	MCI-AD, or mild AD  (MMSE 20-27)  PET positive for amyloid	MCI-AD, mild AD, or moderate AD  (MMSE 16-27)  PET positive for amyloid
Target enrollment (randomization ratio according to doses below)	180  (1:1)	375  (2:2:1)	500 (≥v5.0: 450)  (1:4:4)
Planned doses (sample size)	HMTM 8 mg/day (N=90)  Placebo (N=90)	HMTM 8 mg/day (N=150)  Placebo (N=150)  HMTM 16 mg/day (N=75)	HMTM 8 mg/day (N=50)  Placebo/MTC (N=200)  HMTM 16 mg/day (N=200)

The primary efficacy analysis is performed based on the subjects randomized under protocol version 5.0 or higher, in which some MTC tablets were introduced to placebo treatment kits (on average twice per week spiking) as urinary discolorant to maintain the treatment blinding. In a sensitivity analysis, all randomized subjects are analyzed. Safety assessment will be performed based on all randomized subjects as well.

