## 2.6. Randomization Methodology

With protocol version 5.0 (see Table 1), subjects who satisfied all eligibility criteria were randomized to one of three study regimens HMTM 16 mg/day, HMTM 8 mg/day, or control (4:1:4, at the study- rather than site-level). Randomization was stratified by (**bold** level will be used as reference category in statistical analyses, if needed and results are not population weighted):

Sponsor:	TauRx Therapeutics Ltd.		
Protocol:	TRx-237-039		
Document Version No.:	3.0	Document Date:	07-JUN-2023

---

- Severity (three levels: Mini-Mental State Examination (MMSE) **16-19 (moderate)**, 20-25 (mild), or 26-27 (MCI-AD)),
- Prior use of standard AD treatment (two levels: AChEI/memantine or **none**), and
- Region (two levels: North America or **Europe**).

Global enrollment across the whole study was managed such that subjects were assigned to the Screening MMSE severity groups with a target of approximately 2:3:1 (MMSE 16-19, MMSE 20-25, and MMSE 26-27, respectively) for those randomized under protocol version 5.0 and above. Each stratum was closed when the target enrollment was achieved.

If not indicated otherwise, any analysis or summary that groups subjects by prior use of AChEI and/or memantine, is inclusive of those with a prior history of such use and those who withdrew usage for the purposes of this study (such as lack of efficacy). When data are analyzed descriptively, discontinuation of AChEI and/or memantine before entering the study and discontinuation of AChEI and/or memantine for purposes of study participation (after entering the study) will be differentiated.

If a subject consented to protocol version 2.1 and did not reconsent to a later protocol version, the stratification information provided by the site is considered correct with respect to prior use of AChEI and/or memantine, unless there is specific information in the CRF that contradicts that. In earlier version of the protocol (v2.1), there was no stratum for MMSE as the inclusion criterion was to have an MMSE of 20-25; for all these subjects the stratum will be imputed as MMSE 20-25.

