### 7.3.2. Primary Outcomes

For each of the primary exploratory biomarkers P-tau181 and NfL, an ANCOVA will be used to analyze the change from Baseline at Week 52 visit within each treatment group (HMTM 16 mg/day, HMTM 8 mg/day, and control). In this ANCOVA, the change from Baseline at Week 52 will be compared pairwise

Sponsor:	TauRx Therapeutics Ltd.		
Protocol:	TRx-237-039		
Document Version No.:	3.0	Document Date:	07-JUN-2023

for these three treatment groups. The ANCOVA model will include the randomization stratification variables (see Section 2.6) as fixed factors, the respective efficacy Baseline value as covariate, and the treatment indicator; with the Kenward and Roger method used for calculating the denominator degrees of freedom for the tests of fixed effects. One table will present the LSM for the change from Baseline and the pairwise treatment contrasts at Week 52, and one table will present the p-values of the type 3 tests of the fixed effects along with the estimates of the factors and covariates which are included in the model.

In a sensitivity analysis, subject's age and sex, as well as *ApoE4* carrier status and plasma sample age will be added as further covariates in the primary model. The plasma sample age (of the Week 52 sample) is the difference between the day when the sample was analyzed and the day when the sample was taken + 1. For NfL: a mid-point sample analysis date will be applied, to calculate the plasma sample age. In a second and third sensitivity analysis, Baseline values of MRI whole brain volume and F-FDG-PET temporal lobe glucose uptake normalized to pons will be included separately as covariates as well. Factors with a p-value of 0.2 or smaller will be investigated further upon request.

In addition, this primary model will be repeated with the control group being restricted to the subpopulation with lowest parent MT.

This primary model will be repeated (not including the sensitivity analyses and not including the analysis with respect to the lowest parent MT control group) for the subgroups of the stratification variables region, prior use of AChEI and/or memantine, and Baseline MMSE severity (16-19, and 20-27). For the Baseline MMSE severity, the additional split into the subgroups of scores 16-21, and 22-27 will be done as well. This analysis will also be repeated for the verified AD diagnosis subgroups MCI-AD and probable AD.

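### The exploratory biomarker analysis pools subjects randomized before and after Version 5.0, at different ratios and to different comparators, without a protocol-version term, so the 8 mg contrasts are exposed to era differences

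*SAP*

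**What the plan says.** - **Population (SAP 7.2).** Version 5.0+ subjects who completed the double-blind phase, without those off treatment but on study. Then: "Subjects randomized under a protocol version before version 5 with available biomarker data at Week 52 and completed double-blind treatment phase will be included". No reason is given for adding them.
- **Eras (SAP 1.3, Table 1).** Planned sizes for 8 mg / control / 16 mg are 90 / 90 / none in Version 2.1, 150 / 150 / 75 in Versions 3.0-4.1 and 50 / 200 / 200 from Version 5.0. Control is placebo before Version 5.0 and placebo/MTC from then on. The MMSE range is 20-25, then 20-27, then 16-27. Amyloid-PET positivity is listed from Version 3.0. Double-blind treatment lasts 6, 9 and 12 months. SAP 2.6 confirms the current allocation of 16 mg, 8 mg and control: "4:1:4, at the study- rather than site-level".
- **Model (SAP 7.3.2).** "The ANCOVA model will include the randomization stratification variables", together with the baseline value and treatment, and pairwise contrasts among the three arms. Protocol version does not appear. Plasma sample age enters a sensitivity model here and again in SAP 7.3.5.
- **Main efficacy rule (Protocol 17.4).** Subjects randomized before Version 5.0 are left out of the primary and key secondary analyses: "this is due to the spiking with MTC in the placebo arm".
- **Label.** SAP 7.3: "In the analysis output the control group will be presented as" *MTC 8 mg/week*. SAP 4.6 keeps that label for analyses without earlier subjects and prescribes *Placebo and/or MTC 8 mg/week* where they are included.
- **Status (SAP 7).** Exploratory, with nominal p-values and no multiplicity correction.

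**The concern.** Randomization makes the arms comparable within an era. When eras with unequal allocation ratios are pooled and era is left out of the model, arm and era become associated, and any era difference in biomarker change passes into the arm contrasts. Version 5.0 cut the planned 8 mg share from two fifths to one ninth, so earlier subjects weigh most in that arm.

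The eras differ in control treatment, MMSE range, entry requirements and calendar time. Earlier subjects with a Week 52 sample also had to stay on beyond their original 6 or 9 months, which is selection after randomization.

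At stake is the reading of 8 mg versus control and 16 mg versus 8 mg. SAP 7.3.2 plans both contrasts, and a reader would take them as dose effects. The pooled control group also mixes two randomized comparators under a label that SAP 4.6 assigns to only one of them.

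**Working it through.** **1. The plan's own arm sizes.** 450 × (1, 4, 4)/9 = 50 / 200 / 200, and 375 × (2, 2, 1)/5 = 150 / 150 / 75. Both match Table 1. The documents give no biomarker sample size; SAP 7 refers that to a separate research plan.

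**2. How many earlier subjects?** Total target minus Version 5.0+ target: about 500 − 450 = 50 randomized earlier. Only those who continued to Week 52 under Version 5+ can qualify. Their number is not stated, so the range is 0 to about 50.

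**3. Earlier-era share by arm.** Share = earlier n / (earlier n + Version 5+ n), with the earlier subjects split 2:2:1 and added to 50 / 200 / 200:

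| Added | 8 mg | Control | 16 mg | Gap, 8 mg − control | Gap, 8 mg − 16 mg | Gap, 16 mg − control |
|---|---|---|---|---|---|---|
| 10 | 4/54 = 7.4% | 4/204 = 2.0% | 2/202 = 1.0% | 0.054 | 0.064 | −0.010 |
| 25 | 10/60 = 16.7% | 10/210 = 4.8% | 5/205 = 2.4% | 0.119 | 0.142 | −0.023 |
| 50 | 20/70 = 28.6% | 20/220 = 9.1% | 10/210 = 4.8% | 0.195 | 0.238 | −0.043 |

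If the Version 5+ arms are cut to 75-80% completers, in line with the plan's 20-25% withdrawal, the gaps with 50 added become 0.22-0.23 (8 mg versus control) and −0.05 to −0.06 (16 mg versus control). If all 50 came from Version 2.1 at 1:1, they would be 0.22 and −0.11 on the planned arms.

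**4. Bias and type I error, 8 mg versus control.** Bias = gap × era shift. The assumed shift is 0.5 SD, common to all arms and not absorbed by the covariates. It is illustrative; the documents give no value. SE = √(1/n₈ + 1/n_c) in SD units. Type I error = P(|Z + bias/SE| > 1.96).

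| Added | Bias (SD) | SE | Bias/SE | Type I error |
|---|---|---|---|---|
| 10 | 0.027 | √(1/54 + 1/204) = 0.153 | 0.18 | 5.4% |
| 25 | 0.060 | √(1/60 + 1/210) = 0.146 | 0.41 | 6.9% |
| 50 | 0.097 | √(1/70 + 1/220) = 0.137 | 0.71 | 10.9% |

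**5. Effect of the remedy.** In simulations of a three-arm linear model with severity strata (2,000 runs per setting, era shifts of 0 to 1 SD), a version term or restriction to Version 5+ brought the bias to about zero and type I error to 4.3%-6.1%.

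**6. Price in precision.** With Version 5+ arms at 80% and 50 earlier subjects, the SE of 8 mg versus control is √(1/60 + 1/180) = 0.149 SD as planned, about 0.15-0.16 with the version term, and √(1/40 + 1/160) = 0.177 in Version 5+ subjects only.

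**The case against.** The case on the other side has weight. The analyses are declared exploratory. The count may be small: Version 2.1 and Versions 3.0-4.1 ran for 6 and 9 months, the Week 52 PK samples that serve as the biomarker source (SAP 7.1.1) came in with Version 5.0, and SAP 6.1 speaks of re-consent to Version 5+. With 10 such subjects the distortion is slight. Part of an era effect is already handled, through the severity factor, the repeat in MMSE 20-27, plasma sample age in two sensitivity analyses, and the comparison with controls who have the lowest parent MT. A completer set analysed by treatment received is not a strictly randomized comparison even within Version 5+. The research plan with the rationale is also not available here.

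These points limit the size and priority. They do not supply a version term or a Version-5-only repeat, and sample age is absent from the primary model.

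A reader might infer more than the documents support:
- *That 29% of the 8 mg arm comes from the earlier era, or that the bias reaches about 0.8 SE.* The former needs all of about 50 earlier subjects to have Week 52 samples. The latter needs all 50 to come from the six-month Version 2.1, plus the assumed 0.5 SD shift: 0.222 × 0.5 / 0.133 = 0.83.
- *That earlier controls took true placebo all year, so the label is false for them individually.* SAP 4.6 foresees controls who moved from placebo to MTC, and SAP 6.3 describes controls entering the open-label phase as coming from MTC. What is established is that the label for the pooled group breaks the SAP 4.6 rule.
- *That the main efficacy result is compromised.* The primary efficacy populations are restricted to Version 5.0+.

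**Conclusion.** The point holds as a design weakness of the exploratory biomarker analysis. Subjects from eras with different allocation ratios and different randomized comparators are pooled with no version term, and the control label conflicts with the SAP's own rule. The exposure lies mainly in the 8 mg contrasts. For 8 mg versus control it runs from negligible (about 0.03 SD, type I error 5.4%, with 10 earlier subjects) to material (about 0.10 SD, 11%, with 50), given 2:2:1 allocation and an assumed 0.5 SD era shift; neither the count nor the shift can be taken from the documents. For 16 mg versus control the share gap is at most about 0.04-0.06 at 2:2:1.

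**What to change.** 1. In SAP 7.3.2, add a fixed factor for protocol version at randomization (before 5.0 / 5.0 and above) to the biomarker ANCOVA, and repeat the model in Version 5+ subjects only. The factor removes a shift common to all arms; the repeat gives the contrast without controls who were randomized to placebo. Making Version 5+ the main set, with the pooled set plus the factor as sensitivity analysis, is equally sound.
2. Report the number of earlier subjects by arm, so that readers can place the results within the range above.
3. In SAP 7.3, use the SAP 4.6 label *Placebo and/or MTC 8 mg/week* for every output that includes earlier subjects.

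The cost is SAP wording and one extra model run. For 8 mg versus control, with 50 earlier subjects and 80% completion of the Version 5+ arms, the SE barely changes with the factor (about 0.15-0.16 SD, against about 0.15) and is about 0.18 SD in the Version-5-only model. With fewer earlier subjects the loss from restriction is smaller.
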